2.2 SAFETY OBJECTIVE

The safety objective for this study is to evaluate the safety of RO7198457 plus pembrolizumab compared with pembrolizumab alone on the basis of the following endpoints:

- Incidence and severity of adverse events, with severity determined according to National Cancer Institute Common Terminology Criteria for Adverse Events, Version 5.0 (NCI CTCAE v5.0)
- Change from baseline in targeted vital signs
- Change from baseline in targeted clinical laboratory test results

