3.1.4 Crossover from Control Arm A to Experimental Treatment

Patients in Arm A (pembrolizumab only) with confirmed radiographic disease progression will be permitted to cross over to the experimental treatment (RO7198457 plus pembrolizumab) at the investigator's discretion, after discussion with the Medical Monitor, and the patient meets all of the crossover eligibility criteria in Section 4.1.3. In addition, if a patient in Arm A completes 24 months of pembrolizumab and experiences

confirmed disease progression <6 months after discontinuation of pembrolizumab, the patient may be permitted to receive crossover treatment (RO7198457 plus pembrolizumab) if crossover eligibility criteria are met (see Section 4.1.3). For patients in Arm A who experience confirmed disease progression, an optional tumor biopsy will be collected for patients with a safely accessible site of disease (see Section 4.5.7.2).

Patients must provide consent to acknowledge having had a discussion with the treating investigator of the benefit-risk balance, *including other treatment options (if available)*, before beginning crossover treatment. [REDACTED]

[REDACTED] Refer to [Appendix 2](#) for the schedule of assessments for crossover patients.

A radiographic tumor assessment must also be performed, unless already done to document disease progression within 6 weeks prior to starting crossover treatment. The radiographic tumor assessment at the time of disease progression/recurrence will become the new baseline for future response assessments.

Crossover treatment should begin no later than [REDACTED] after the last dose of prior study treatment on Study GO40558. In patients with confirmed disease progression <6 months after discontinuation of pembrolizumab therapy, crossover treatment should begin within [REDACTED] of confirmed progression.

Patients who cross over to the combination of RO7198457 plus pembrolizumab will continue treatment for up to 12 months as long as they are experiencing clinical benefit as assessed by the investigator. Patients with confirmed disease progression after crossing over from Arm A to Arm B may be considered for treatment beyond disease progression provided that criteria for treatment beyond disease progression are met as specified in Section 3.1.3. Patients will be evaluated for safety and efficacy according to the schedules of activity described in [Appendix 2](#).

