4.1.3.1 Inclusion Criteria for Crossover Treatment

- Confirmed progression of disease as assessed by investigator per RECIST v1.1 after at least one dose of pembrolizumab in Arm A

Disease progression must be confirmed by a consecutive assessment ≥ 4 weeks from the date first documented.

Patients who complete 24 months of pembrolizumab and experience disease progression < 6 months after discontinuing pembrolizumab may also be eligible to cross over.
- ECOG Performance Status of 0 or 1 (see [Appendix 6](#))
- For women of childbearing potential: agreement to remain abstinent (refrain from heterosexual intercourse) or use contraceptive measures, and agreement to refrain from donating eggs, as defined below:

Women must remain abstinent or use contraceptive methods that result in a failure rate of $< 1\%$ per year during the treatment period and for at least 90 days

after the final dose of RO7198457 and at least 4 months after the final dose of pembrolizumab, whichever occurs later. Women must refrain from donating eggs during this same period.

A woman is considered to be of childbearing potential if she is postmenarcheal, has not reached a postmenopausal state (≥ 12 continuous months of amenorrhea with no identified cause other than menopause), and is not permanently infertile due to surgery (i.e., removal of ovaries, fallopian tubes, and/or uterus) or another cause as determined by the investigator (e.g., Müllerian agenesis). The definition of childbearing potential may be adapted for alignment with local guidelines or requirements.

Examples of contraceptive methods with a failure rate of $< 1\%$ per year include bilateral tubal ligation, male sterilization, and established proper use of hormonal contraceptives that inhibit ovulation, hormone-releasing intrauterine devices, and copper intrauterine devices.

Hormonal contraceptive methods must be supplemented by a barrier method plus spermicide.

The reliability of sexual abstinence should be evaluated in relation to the duration of the clinical trial and the preferred and usual lifestyle of the patient. Periodic abstinence (e.g., calendar, ovulation, symptothermal, or postovulation methods) and withdrawal are not acceptable methods of contraception.

If required per local guidelines or regulations, locally recognized acceptable methods of contraception and information about the reliability of abstinence will be described in the local Informed Consent Form.

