4.1.3.2 Exclusion Criteria for Crossover Treatment

- Toxicity experienced while on study treatment in the control arm that would require permanent discontinuation of pembrolizumab or preclude treatment with the combination of RO7198457 and pembrolizumab in the Arm B portion of the study.

- Tumor progression at critical anatomical sites that cannot be readily managed and stabilized by protocol-allowed medical interventions prior to repeat dosing

Critical anatomical sites include the CNS, central airway, the great vessels, and other organs or tissues where compromised function secondary to tumor progression would be expected to result acutely in severe and/or irreversible disability or death.

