6.4.1 Primary Efficacy Endpoint of PFS

PFS is defined as the time from randomization to the date of first documented disease progression or death, whichever occurs first. Disease progression for PFS analysis will be determined on the basis of investigator assessment using RECIST v1.1. The primary PFS analysis will occur after approximately 80 events have been observed in the primary population or approximately 24 months from FPI.

Data for a patient without disease progression or death as of the clinical data cutoff date will be censored at the time of the last tumor assessment (or at the date of randomization plus 1 day if no tumor assessment was performed after the baseline visit). Data from a patient who is lost to follow-up will be included in the analysis and censored on the last date of tumor assessment that the patient was known to be progression free.

Kaplan-Meier methodology will be used to estimate the PFS curve and median PFS for each treatment arm. A stratified Cox proportional-hazards model will be used to estimate the HR and its 95% CI. The two-sided stratified log-rank test will be used to compare PFS between the two treatment arms at the two-sided significance level of 5%. Unstratified modeling approaches may be used to assess the robustness of the PFS primary endpoint results. To account for patients who may discontinue study treatment prior to first administration of RO7198457, a landmark analysis restricted to patients treated at Cycle 2 and beyond may be performed with PFS time calculated starting from Cycle 2, Day 1 on the ITT and modified subsets.

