6.5 SAFETY ANALYSES

Safety analyses will be conducted in all randomized patients who received at least one dose of RO7198457 and/or pembrolizumab. Safety analyses will be performed by treatment arm and will be based on actual treatment received. Specifically, a patient will be included in the RO7198457 plus pembrolizumab arm in the safety analyses if the patient receives any amount of RO7198457, regardless of the initial treatment assignment at randomization.

Safety endpoints will include incidence and severity of adverse events (using NCI CTCAE v5.0), including serious adverse events and adverse events of special

interest, changes from baseline in clinically relevant vital signs, physical findings, and clinical laboratory results following the administration of RO7198457 plus pembrolizumab or solely pembrolizumab. Drug exposure will be summarized, including duration, dosage, and dose intensity. Verbatim description of adverse events will be mapped to the MedDRA thesaurus terms and graded according to the NCI CTCAE v5.0.

All adverse events that occur during or after the first study treatment, until 90 days after the final dose of study drug or initiation of another systemic anti-cancer therapy, whichever occurs first, will be summarized by treatment arm and NCI CTCAE grade. In addition, serious adverse events and adverse events leading to study treatment discontinuation or interruption will be summarized accordingly. Multiple occurrence of the same event will be counted once at the maximum severity. Laboratory data with values outside of the normal ranges will be identified. Additionally, selected laboratory data will be summarized by treatment arm and grade. Vital signs will also be summarized by treatment arm and visit. Deaths and causes of deaths will be summarized. Analyses of safety endpoints will be conducted at the time of the primary efficacy analysis.

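### Section 6.5 moves Arm A patients dosed at crossover, with the adverse events they had on pembrolizumab alone, into the combination arm, which biases the by-arm safety comparison

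*Combined protocol and SAP*

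**What the plan says.** Section 6.5 analyses safety by arm according to treatment actually received. A patient belongs to the combination arm "if the patient receives any amount of RO7198457, regardless of the initial treatment assignment at randomization". The events summarised are "All adverse events that occur during or after the first study treatment, until 90 days after the final dose of study drug", or until another systemic anti-cancer therapy starts if that is earlier. A repeated event counts once, at its worst grade. On timing, "Analyses of safety endpoints will be conducted at the time of the primary efficacy analysis", and under Section 6.4.1 that analysis comes "after approximately 80 events have been observed in the primary population or approximately 24 months from FPI".

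Crossover is part of the design. Section 3.1.4: "Patients in Arm A (pembrolizumab only) with confirmed radiographic disease progression will be permitted to cross over to the experimental treatment". Three conditions decide who is dosed:

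- Section 4.1.3.1: "Disease progression must be confirmed by a consecutive assessment", at least 4 weeks after progression is first documented.
- Section 4.1.3.2 excludes patients with "Toxicity experienced while on study treatment in the control arm that would require permanent discontinuation of pembrolizumab".
- Appendix 2, footnote a, keeps patients on pembrolizumab alone until their vaccine is ready.

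No section exempts crossover patients from the 6.5 rule, ends their Arm A event window at crossover, or plans a crossover safety summary. The new baseline in Section 3.1.4 is for tumour response. The crossover analysis in Section 6.4.2 covers response rate only; the patient-reported outcomes paragraph lists crossover merely as a timepoint.

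**The concern.** Section 2.2 makes the comparison explicit: "The safety objective for this study is to evaluate the safety of RO7198457 plus pembrolizumab compared with pembrolizumab alone". Under the 6.5 rule, membership of the two safety arms depends on what happens after randomisation: progression, survival and follow-up to the first vaccine dose, absence of disqualifying toxicity, and choice. The event window opens at the first pembrolizumab dose, so a patient who moves brings along events that occurred before any RO7198457.

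The direction differs by type of event:

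- **Toxicity that stops pembrolizumab.** Affected Arm A patients cannot leave, while unaffected ones can. The control rate rises and RO7198457 looks safer. Section 6.5 itself plans a table of events leading to discontinuation.
- **Non-fatal events recorded around progression.** Section 5.3.5.10 has events reported when it is uncertain whether progression caused them. Only progressors move, so these events go to the combination column.
- **Deaths.** Section 5.3.5.8 has deaths in the reporting period, including melanoma deaths, recorded as adverse events. A patient must live to the first crossover dose in order to move, which pulls one way; deaths after crossover pull the other.

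Pooling also leaves no planned table on tolerability of RO7198457 after progression, which Section 3.3.7 gives as a reason for offering crossover.

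**Working it through.** The plan states no crossover fraction, adverse event rate or safety-arm size, so there is no figure to reproduce. What follows is an illustration under no true difference. Differences are combination minus pembrolizumab; negative favours RO7198457.

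**From the documents.** 40 patients in Arm A and 80 in Arm B, 18-month accrual (Section 6.1); control median PFS 5–6 months (Section 3.3.6), taken as 5.5; cutoff at about 80 events or 24 months (Section 6.4.1).

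**Assumed.** Crossover uptake 40–60% of eligible progressors; 2.5 months from progression to first crossover dose (the permitted interval is redacted); 10% of PFS events are deaths; 20% otherwise ineligible; 15% of patients susceptible to toxicity that stops pembrolizumab, mean onset 2 months; event window closing 3 months after the PFS event; crossover median PFS 3 months.

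**Step 1: the mechanism in whole patients.** Let 15% have the toxicity in each arm, with it barring crossover. Arm A has 0.15 × 40 = 6 cases and Arm B has 0.15 × 80 = 12. Let 16 patients cross over and have the same 15% risk afterwards.

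- Pembrolizumab: 6/(40 − 16) = 25%.
- Combination: (12 + 0.15 × 16)/(80 + 16) = 14.4/96 = 15%.

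With 8 crossovers the control rate is 6/32 = 18.8%; with 24 it is 6/16 = 37.5%. The combination stays at 15%. Keeping patients where they were randomised gives 6/40 and 12/80, both 15%.

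**Step 2: how many move by month 24, exponential PFS.** The hazard is λ = ln 2/5.5 = 0.126 per month. Follow-up f is uniform on 6 to 24 months. The chance that progression plus 2.5 months falls before cutoff is

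1 − [exp(−3.5λ) − exp(−21.5λ)]/(18λ) = 0.746.

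Alive at progression and otherwise eligible: 40 × 0.746 × 0.90 × 0.80 = 21.5. The share still free of stopping toxicity at the crossover dose is about 1 − 0.15 × [1 − 0.126/(0.126 + 0.5) × exp(−1.25)] = 0.86. So 21.5 × 0.86 = 18.5, and 40/50/60% uptake gives 7.4, 9.2 and 11.1 patients. The simulation gives 7.4, 9.3 and 11.1.

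**Step 3: simulated difference in stopping toxicity (20,000 trials per main cell; uptake 40/50/60%).**

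| Cutoff and PFS model | Patients moved | Difference, points | SD, points |
|---|---|---|---|
| Month 24, exponential (98 events) | 7.4/9.3/11.1 | −4.3/−5.6/−6.9 | 7.6–8.3 |
| 80 events (month 19.3), exponential | 5.4/6.7/8.1 | −2.8/−3.6/−4.5 | 7.2–7.5 |
| Month 24, 28% plateau (about 80 events) | 6.3/7.9/9.5 | −3.4/−4.5/−5.6 | 7.4–7.9 |

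The plateau model keeps the same median, meets both triggers in Section 6.4.1, and reflects the plateaus described in Section 1.4. In the first row at 50% uptake, Arm A shows 18.5% and the combination 13.0%. The shift scales with the susceptible share: 1.0–2.6 points at 5%, 4.2–10.0 at 25%. With the Arm A window closed at crossover, every cell is within 0.2 points of zero.

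**Step 4: other event types, rule as written.**

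- Non-fatal events recorded around progression in 10–30% of progressors: +0.9 to +5.0; within 0.1 of zero with the window closed.
- Deaths inside the event window: −7.0 to 0.0. All deaths to cutoff: −6.1 to +4.8; within 0.4 of zero by randomised arm.
- Events unrelated to progression or stopping: the rule changes the crude difference by −2.0 to +1.6.

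**The case against.** The any-amount sentence may have been written for dosing errors. Section 6.5 also speaks of results following the combination or pembrolizumab alone, which is compatible with attribution by treatment period, and Section 5.1.4.3 and Appendix 2 name crossover as its own setting. On that view the plan is silent about crossover and has not decided to pool. But the wording on results lists endpoints and gives no rule for splitting a patient's events, whereas the membership sentence is explicit and unrestricted. A programmer following the text would pool.

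The objections to size stand in part. Uptake, lag, eligibility and toxicity rates are all assumed. At 20% uptake the plateau model gives only about 1.9 points. The exponential model at month 24 yields 98 events where the plan expects about 80. It also runs ahead of Section 6.8.1, with about 61 events at month 16 and 73 at month 18 (51% and 60% of 120 patients), against 25% and 50% maturity planned for about those times. Accrual weighted later, with the Week 12 scan schedule, gives about 3.6 to 4.3 points at 50% uptake. Section 5.3.5.10 keeps events clearly due to progression out of the adverse event data, which limits the progression-related shift.

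The study is hypothesis-generating, safety is descriptive and efficacy is by intention to treat, so the consequence is limited. None of this removes the defect in the membership rule.

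**Conclusion.** The concern holds. Applied as written, Section 6.5 lets events after randomisation decide safety-arm membership and attributes events on pembrolizumab alone to the combination. Confidence is high on the text and on the direction for stopping toxicity, which follows from the crossover exclusion. The direction for deaths is not determined.

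The size is illustrative: 2.8 to 6.9 points in favour of RO7198457 for stopping toxicity at 40–60% uptake and 15% susceptible, or 3.4 to 5.6 in the model that meets both analysis triggers. That is smaller than the 7–8 point SD of a single trial, but it is systematic and falls on the stated safety comparison with only about 40 controls. It should be fixed before the safety analysis.

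**What to change.** Amend Section 6.5:

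1. For the by-arm comparison, keep Arm A patients in Arm A and close their adverse event window at the first crossover dose of RO7198457.
2. Summarise events from that dose onward as a separate crossover group, not pooled with Arm B.
3. Limit the any-amount rule to dosing departures outside the planned crossover.
4. Add exposure-adjusted rates, because closing the window shortens Arm A follow-up. For unrelated events the closed-window rate ratio was 0.98–1.01 in simulation.
5. Summarise all deaths by randomised arm, flagging those after the first crossover dose. Closing the window alone leaves −0.3 to +2.6 points for deaths inside it.

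Optionally, add one sentence on where Arm B patients who never receive RO7198457 are counted; Section 6.4.1 foresees such patients.

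The cost is SAP wording, one treatment-period flag in the adverse event datasets and a few extra tables. No new data are needed.

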6.6 PHARMACOKINETIC ANALYSES

The PK analysis population will consist of patients with any blood sample drawn according to [Appendix 3](#) for the purpose of PK analysis. Individual and mean plasma [REDACTED] concentrations (minimum serum concentration observed [C_{min}] and maximum serum concentration observed [C_{max}]) will be tabulated and summarized for each cycle for which pharmacokinetics are to be measured. Data will be pooled with data from the Phase Ia/Ib study (GO39733) using an established population PK model to estimate total AUC, total CL, V_{ss} , and terminal half-life (as appropriate for data collected). Estimates for these parameters will be tabulated and summarized (mean, standard deviation, coefficient of variation [%CV], median, range, geometric mean, and geometric mean CV [%CV]) by treatment arm, when appropriate and as data allow. Inter-patient variability and drug accumulation will be evaluated.

Serum pembrolizumab concentration data (C_{max} and C_{min}) will be tabulated and summarized for each cycle where collected. Descriptive statistics will include geometric mean and geometric mean CV, as appropriate. Pembrolizumab concentration data may be pooled with data from other studies using an established population PK model to estimate total AUC, as warranted by the data. Data may be compared with historical data, as these results will provide preliminary information on whether [REDACTED] pembrolizumab pharmacokinetics are altered by co-administration of the other agent.

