2.3 PHARMACOKINETIC OBJECTIVES

The exploratory PK objectives for this study are as follows:

- To characterize the RO7198457 PK profile on the basis of the following endpoints:
 - Plasma concentrations [REDACTED] at specified timepoints
 - Plasma concentrations [REDACTED] at specified timepoints
- To characterize the PK of pembrolizumab when given in combination with RO719847 on the basis of the following endpoint:
 - Serum concentrations of pembrolizumab at specified timepoints
- To evaluate potential relationships between drug exposure and the efficacy and safety of RO7198457 and pembrolizumab on the basis of the following endpoints:
 - Relationship between plasma concentration or PK parameters [REDACTED] and efficacy endpoints
 - Relationship between plasma concentration or PK parameters [REDACTED] and efficacy endpoints
 - Relationship between plasma concentration or PK parameters [REDACTED] and safety endpoints
 - Relationship between plasma concentration or PK parameters [REDACTED] and safety endpoints

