Appendix 1: Schedule of Activities: Arm A (Pembrolizumab) (cont.)
Screening Parts A and B and Cycles 1–12

	Screening Period ^a			Treatment Period (Initial)					UV ^b
	Part A	Part B		Cycle 1	Cycle 2	Cycles 3, 5, 7	Cycles 4, 6	Cycles 9, 11	
Day (Window)		–28	–14	1 (±2)	1 (±2)	1 (±2)	1 (±2)	1 (±3)	1 (±3)
Serum/plasma chemistry ^r	x ^r		x	x	x	x	x	x	x
Coagulation (PT, aPTT, INR)			x						
Amylase, lipase			x		x		x		x
Urinalysis ^s			x		x		x (C6 only)		x (C10 only)
Pregnancy test ^t			x		x		x		x
Serum ferritin and CRP ^u			x		x	x		x	
TSH, free T3, and free T4 ^v			x				x (C4 only)		x (C8 and C12 only)
Autoantibody tests ^w			x						
HBV, HCV, HIV, TB serology tests ^x	x								
Cancer-related procedures ^y				x	x	x	x	x	x
EORTC scales ^z				x	x	x	x	x	x
PRO-CTCAE scales and single-item bother ^z				x	x	x	x	x	x
WPAI ^{aa}				x			x (C4 only)		
Pembrolizumab infusion ^{bb}				x	x	x	x	x	x
Serum (pembrolizumab) PK sample	See Appendix 3								

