PP After study treatment completion or discontinuation, information on survival status, new anti-cancer therapy (including targeted therapy and immunotherapy), and cancer-related procedures will be collected via telephone calls, patient medical records, and/or clinic visits approximately every 3 months until death (unless the patient withdraws consent or the Sponsor terminates the study). If a patient requests to be withdrawn from follow-up, this request must be documented in the source documents and signed by the investigator. If the patient withdraws from study, study staff may use a public information source (e.g., county records) to obtain information about survival status only.

Appendix 3

Schedule of Pharmacokinetic and Biomarker Samples

		Treatment Period								TX DC	FU
		Initial						Maintenance ^a			
Cycle	Cycle 1	Cycle 2		Cycle 3 ^b		Cycle 4	Cycles 5, 6, 7	Cycles 13, 21, 29			
Days (window)	1 (± 2)	1 (± 2)	8 (± 2) ^c	15 (± 2) ^c	1 (± 2)	8 (± 2)	1 (± 2)	1 (± 2)	1 (± 3)		
Serum pembrolizumab PK sample ^{e, f}	Pre-dose, and 30 (± 5) min after pembro infusion	Pre-dose					Pre-dose				2 months post EOT (± 1 week) ^f
Plasma Biomarker (Cytokines) (safety run-in, Arm B, and crossover only) ^{g, h}	Pre-dose, 4–6 hr post-dose		Pre-dose, 4–6 hr post-dose	Pre-dose, 4–6 hr post-dose	Pre-dose, 4–6 hr post-dose	Pre-dose, 4–6 hr post-dose	Pre-dose, 4–6 hr post-dose	C5, C6, C7: pre-dose, 4–6 hr post-dose	Pre-dose, 4–6 hr post-dose		
Blood Biomarker (ctDNA)	Pre-dose							C7D1 only (pre-dose)	C13D1 only (pre-dose)		

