Appendix 3: Schedule of Pharmacokinetic, Immunogenicity, and Biomarker Samples (cont.)

C=cycle;
min=minutes; mos=months;

OT=end of treatment; FU=Follow-Up; hr=hours;

PK=pharmacokinetic; TX DC=treatment discontinuation.

a [REDACTED]

b [REDACTED]

c [REDACTED]

d [REDACTED]

- e Pre-dose pembrolizumab PK collections are to be collected just prior to infusion of pembrolizumab. Post-dose collections are to be collected after infusion of pembrolizumab is completed. On the days that pembrolizumab is given on the same day as RO7198457, post-dose collections are to be collected 30 (± 5) min after infusion of pembrolizumab is completed and before starting infusion of RO7198457 RNA-A.
- f Serum pembrolizumab PK collection will be collected at 2 months post end of treatment *unless pembrolizumab is administered as a new anti-cancer therapy.*
- g At C1D1 (pembrolizumab monotherapy), plasma cytokines sample will be collected prior to pembrolizumab administration and 4–6 hours after infusion of pembrolizumab. For the subsequent cycles, a plasma cytokines sample will only be collected on the days of RO7198457 infusion, regardless of the pembrolizumab cycle and day. Pre-dose sample will be collected prior to infusion of any study drug. Post-dose collections are to be collected 4–6 hours after infusion of RO7198457 RNA-B is completed. NOTE: Pre-and postdose plasma for biomarker cytokines do not need to be drawn if RO7198457 is not available for dosing, except on C1D1.
- h Ad hoc plasma cytokine levels may be drawn once daily in patients experiencing Grade ≥ 2 cytokine release syndrome, infusion-related reaction, or flu-like symptoms.

Appendix 4

Response Evaluation Criteria in Solid Tumors (RECIST v1.1)

Selected sections from the Response Evaluation Criteria in Solid Tumors (RECIST), Version 1.1¹ are presented below, with slight modifications and the addition of explanatory text as needed for clarity.²

MEASURABILITY OF TUMOR AT BASELINE

DEFINITIONS

At baseline, tumor lesions/lymph nodes will be categorized as measurable or non-measurable as follows.

a. Measurable Tumor Lesions

Tumor Lesions. Tumor lesions must be accurately measured in at least one dimension (longest diameter in the plane of measurement is to be recorded) with a minimum size of:

- 10 mm by computed tomography (CT) or magnetic resonance imagining (MRI) scan (CT/MRI scan slice thickness/interval no greater than 5 mm)

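### Section 6.6 names only an optional historical reference for the pembrolizumab interaction question and calls for no by-arm summary, although randomised Arm A is sampled on the same PK schedule

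*Combined protocol and SAP*

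**What the plan says.** - **Objective.** Section 2.3 lists, among exploratory PK objectives, "To characterize the PK of pembrolizumab when given in combination with RO719847" (the compound number is misspelt there). The endpoint is serum pembrolizumab concentration at specified timepoints. No contrast with Arm A is mentioned.
- **Analysis.** Section 6.6 says that pembrolizumab Cmax and Cmin "will be tabulated and summarized for each cycle where collected". Pooling with other studies in a population PK model is optional. The interaction sentence then reads "Data may be compared with historical data, as these results will provide preliminary information on whether", followed by a blacked-out gap and a reference to pembrolizumab PK. The phrase "by treatment arm, when appropriate and as data allow" is in the preceding paragraph, which deals with the redacted plasma analyte. It is not repeated for pembrolizumab.
- **Sampling.** Both parts of the Arm A schedule in Appendix 1 carry a row "Serum (pembrolizumab) PK sample" that points to Appendix 3. The Appendix 3 cytokine row is limited to the groups that receive RO7198457. The pembrolizumab row has no such limit. Its first cell reads "Pre-dose, and 30 (± 5) min after pembro infusion".
- **Footnote e to Appendix 3.** "On the days that pembrolizumab is given on the same day as RO7198457, post-dose collections are to be collected" 30 (±5) minutes after the pembrolizumab infusion ends and before the RO7198457 infusion starts.

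**The concern.** A historical reference mixes any RO7198457 effect with differences between studies in assay, population, disease burden and prior adjuvant anti-PD-1 exposure, which Section 4.1.1 allows under conditions. Section 1.4 raises the same kind of worry about historical controls as a reason to randomise, though it does so for efficacy and not for PK. Here a randomised group on pembrolizumab alone is already being sampled, so the cleaner comparison is available and simply not written down.

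The second issue is which sample can answer the question. If pembrolizumab Cmax is tabulated for the combination arm without a label, a reader of the study report could take it as evidence on the interaction, when on the legible schedule it is measured before any RO7198457 is given.

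**Working it through.** The plan states no sample size, power or precision for PK, so there is no figure to reproduce. The check is a reading of the schedule followed by an illustrative precision calculation.

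**Step 1: which samples exist.** The day row of Appendix 3, plus the discontinuation and follow-up columns, gives 11 visit columns. The pembrolizumab and cytokine rows each have 11 cells.

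| Visit | Pembrolizumab PK | Cytokines (RO7198457 groups) |
|---|---|---|
| C1D1 | pre-dose and 30 min post-infusion | yes |
| C2D1 | pre-dose | blank |
| C2D8, C2D15, C3D1, C3D8 | blank | yes |
| C4D1 | pre-dose | yes |
| Cycles 5–7 | blank | yes |
| Cycles 13, 21, 29 | blank | yes |
| Discontinuation | blank | blank |
| Follow-up | 2 months after end of treatment | blank |

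**Step 2: which samples can follow RO7198457.**
- *C1D1.* Section 3.1.1 puts at least one 21-day cycle of pembrolizumab alone before RO7198457 in Arm B and in the run-in, and footnote g describes C1D1 as a monotherapy day. The one post-infusion sample therefore comes at least 21 days before the earliest RO7198457 dose.
- *C2D1 pre-dose.* This also appears to precede RO7198457. After C1D1, footnote g ties cytokine draws to RO7198457 days, and the first filled cell after C1D1 is C2D8. Even if RO7198457 were given on C2D1, the sample is drawn just before pembrolizumab, which Section 4.3.2 places ahead of RO7198457.
- *C4D1 pre-dose.* The cytokine row implies four RO7198457 visits before it (C2D8, C2D15, C3D1, C3D8), provided the product is available. This is the only scheduled on-treatment sample that can reflect co-administration.
- *Two months after treatment.* This also follows RO7198457, but it is off treatment and is not a Cmax sample.

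**Step 3: is Arm A still a clean control at C4D1?** C4D1 falls 3 × 21 = 63 days (9 weeks) after C1D1. The first scheduled scan is at Week 12, and Section 4.1.3.1 requires progression confirmed at least 4 weeks later before crossover. On schedule, no Arm A patient has crossed over by C4D1.

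**Step 4: precision of a concurrent comparison.** Inputs: 120 patients at 2:1 give 80 and 40 (Section 6.1). The between-patient CV (30% to 60%) and a 25% loss of samples (60 and 30) are assumptions, because the documents give neither.

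SD on the log scale = √ln(1 + CV²), which is 0.294 at 30% and 0.555 at 60%.

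90% CI factor = exp[1.645 × SD × √(1/n_B + 1/n_A)].

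- 80 vs 40: √(1/80 + 1/40) = 0.194. CV 30%: exp(1.645 × 0.294 × 0.194) = 1.10. CV 60%: exp(1.645 × 0.555 × 0.194) = 1.19.
- 60 vs 30: √(1/60 + 1/30) = 0.224. CV 30%: 1.11. CV 60%: 1.23.

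Power to detect a ratio of 0.80 at two-sided 5%, for CV 30%, 40%, 50% and 60%:

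- 80 vs 40: 97%, 85%, 68% and 55%.
- 60 vs 30: 93%, 74%, 56% and 44%.

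**Step 5: dilution.** If only a fraction f of sampled Arm B patients had RO7198457 before C4D1, a true ratio of 0.80 appears as roughly 0.80^f: 0.80 at f = 1, 0.85 at f = 0.75 and 0.89 at f = 0.5. The fraction f is unknown and these values are only a range.

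**The case against.** **The historical sentence may be needed.** It contains a redaction just before pembrolizumab is named, and it ends by referring to the partner drug in general terms. It may therefore also cover the RO7198457 analyte. This trial has no arm on RO7198457 alone, so for that analyte outside data would be the only reference. This stands. A reader might infer that the sentence should be deleted or replaced, and the documents do not support that.

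**The plan does not commit to a historical comparison.** The wording is permissive and preliminary, and the PK population is anyone sampled under Appendix 3, which includes Arm A. This also stands. A reader might infer that an Arm A comparison has been ruled out, but it is only unstated.

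**Nothing says that Cmax will be used to judge the interaction.** Correct. The objective's endpoint is concentrations, and Cmax is tabulated only for cycles where it is collected, which on the legible table means Cycle 1. What remains is a labelling point.

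**The table was read by machine and part of Appendix 3 is blacked out.** The cycle header is broken, footnotes a to d are redacted, and footnote e expects post-dose draws on shared-infusion days. A reader might infer that no post-infusion sample is intended during combination treatment. The documents do not settle this. They show that the legible row and footnote e disagree.

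**Restricting Arm B to patients already dosed would select after randomisation.** Agreed, so the main comparison must use all sampled patients in both arms.

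**Conclusion.** The point holds as an omission. For pembrolizumab, Section 6.6 names only an optional historical reference and calls for no summary by arm, while samples from a concurrent randomised control are already scheduled. On the legible schedule, Cmax is a Cycle 1 monotherapy value, C4D1 pre-dose is the one on-treatment sample that can reflect co-administration, and footnote e's rule has no sample to apply to.

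Under the assumed CV of 30% to 60%, the concurrent ratio would be estimated to within a 90% CI factor of about 1.10 to 1.19 (80 vs 40) or 1.11 to 1.23 (60 vs 30). That is informative for estimation. It is not a powered test: with 60 vs 30 and a CV of 50% or more, a ratio of 0.80 would be detected 56% of the time or less. Precision for the already-dosed subset cannot be given, because its size is unknown.

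Severity is low. The objective is exploratory and the primary PFS conclusion is unaffected. The reading rests on the cell alignment of the Appendix 3 table and would change if footnote e reflects samples that the row was meant to show.

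**What to change.** 1. Keep the historical sentence in Section 6.6 as supportive, and add:

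> Serum pembrolizumab concentrations will be summarised by treatment arm. The C4D1 pre-dose concentration will be compared between all sampled Arm B and all sampled Arm A patients as a geometric mean ratio with 90% CI. A sensitivity analysis will be restricted to Arm B patients who received RO7198457 before that sample.

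2. State that pembrolizumab Cmax is a Cycle 1 monotherapy parameter and does not inform the interaction.
3. Reconcile footnote e with the pembrolizumab row of Appendix 3. If the row is found to be incomplete, revise item 2 to match.

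The cost is a few sentences and one summary table. No new samples or visits are needed. The downside is that Arm B patients not yet dosed with RO7198457 by C4D1 pull the main comparison towards no difference. The sensitivity analysis addresses this, but it is no longer a fully randomised contrast, so the two should be reported together.
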